10.4.3. Premature Termination or Suspension of Study

Notification of all study subjects. No further data collection.

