4. PROTOCOL SUMMARY

Title:	Magnetically Controlled Capsule For Assessment Of Gastric Mucosa In Symptomatic Patients: “MAGNET”
Précis:	This is a single-center prospective study examining the diagnostic utility of a single-use ingestible magnetically controlled capsule (MCC) endoscope (NaviCam™, AnX Robotica) which is remotely controlled by external hardware and software to visualize the mucosa of the stomach on patients with upper abdominal symptoms. Participants will be enrolled and tested at a central site referred from Emergency Departments (EDs), urgent cares (UCs) and primary care practices (PCPs) in the Washington, DC area and additional site(s) to be named. Total enrollment is estimated to be 72 patients with a goal of following all patients with a traditional endoscopy to confirm findings. Aim 1 is to establish feasibility of this novel outpatient testing. Aim 2 is to demonstrate high-quality visualization of gastric anatomic landmarks. Aim 3 is a pilot study to compare visualization of gastric anatomic landmarks and lesions of MCC follow-up traditional EGD. We currently anticipate enrolling 2-3 patients per week over 30 weeks.
Objectives:	
Aim 1: We aim to demonstrate feasibility of MCC in an outpatient primary and urgent care setting. Measured outcomes include duration of MCC test, linkage with EGD follow-up, image storage, image transfer, technician learning curve and documentation.
 
Aim 2: We aim to show that MCC can identify and photograph regions of stomach consistent with established visualized scoring systems for anatomic landmarks.
 
Aim 3: Pilot assessment of MCC compared to subsequent EGD to detect anatomic regions and gastric mucosal lesions.

Population:	An unselected pool of adult patients with an appropriate indication for upper endoscopy such as epigastric pain/burning, nausea and or vomiting, bloating, heartburn, iron deficiency anemia, unintended weight loss, abnormal imaging suggesting organic disease. In general, participants will be age ≥ 18 , mixed gender, mixed race, hemodynamically stable with possible co-morbidities.
Site Number	1
Study Duration:	Time needed to reach sufficient study subjects plus additional time for analysis
Subject Duration:	30 days
Estimated Time to Complete:	12 months

5. SCHEMATIC OF STUDY DESIGN:

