7.2. Secondary Objective

- 1) To perform a cost-effective analysis of MCC v EGD.
- 2) To measure patient satisfaction for EGD v MCC.
- 3) To measure 30-day safety.
- 4) To compare international trials that compared EGD to MCC for detection of gastric lesions.
- 5) To measure the time required to visualize the stomach for MCC versus EGD.

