8. STUDY OUTCOME MEASURES

8.1. Primary Outcome:

Aim 1: Pilot and Feasibility Stage.

- 1) *Implementation:* Installation, Training, Site Requirements
- 2) *Practicality:* Duration of MCC test (minutes), Technician “learning curve,” Clinical Staff and Patient Satisfaction, Duration of fasting required
- 3) *Integration:* Scheduling MCC, Linkage with EGD follow-up, Image storage, Image transfer, Documentation of Interpretation, Photo-documentation, Database development

Aim 2: High-Quality Visualization (90%) of Gastric Anatomic Landmarks

Defined as visualization and photo-documentation of the following anatomical landmarks:

- 1) Lower Esophagus / Z line
- 2) Cardia / fundus
- 3) Body, lesser curvature AND/OR Body, greater curvature
- 4) Anterior / Posterior walls
- 5) Angularis
- 6) Antrum
- 7) Pylorus
- 8) Duodenal Bulb
- 9) Duodenal Ampulla

Aim 3: MCC versus EGD for visualization of anatomic landmarks (see above) and gastric lesions in symptomatic patients

Defined as visualization and photo-documentation of the following structures and diseases:

- 1) Visible Lesions (Paris Classification if relevant)
- 2) Ulcers (Forrest Classification) erosions
- 3) Gastric Atrophy
- 4) Gastric Varices
- 5) Gastritis*
- 7) Submucosal lesions
- 8) “Does patient need a follow-up EGD?” Y/N (Opinion of endoscopist interpreting MCC based on MCC findings.)

* (not erythema but ‘chicken wire’ pattern intramucosal change in vascular pattern or hemorrhagic)

8.2. Secondary Outcomes:

- (1) Cost-effective analysis

- (2) 30-day follow-up for adverse events and safety
- (3) Patient Satisfaction of MCC versus EGD
- (4) Replication of similar sensitivity and specificity of MCC to EGD to prior trials outside of the US for (a) Ulcers; (b) Cancer; (c) Inflammatory Changes
- (5) Time spent visualizing the stomach for MCC versus EGD (minutes)
- (6) Visualization of the duodenum
- (7) Hiatus hernia

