will be pre-determined, and each area will have a predetermined number of images obtained as suggested by Gastroenterology Society guidelines.

5. Patient data collected will include the following elements: chief complaint of patient, history of present illness, past medical history, current medications (only PPIs and pain medication)..
6. At completion of MCC, video will be archived and patient satisfaction will be assessed. Capsule endoscopy will NOT be used for clinical decisions.
7. Patients will be instructed to return to the physician sooner, if concerning signs develop. A 7 and 30-day follow-up call and chart review is only performed if person is lost to follow-up will be conducted to check for symptom resolution and adverse events.
8. Esophagogastroduodenoscopy (EGD) will be performed as soon as possible in an appropriate endoscopy facility by an experienced endoscopist.
9. Endoscopic images will be stored in secure serve for later comparison with MCC images.

Summary of Research Strategy

- ❖ PRE-SCREEN (DAY -7 to DAY -1)
 - Upper Abdominal Pain or Related Symptoms (Indications for an EGD)
 - Performed in ED, UC, PCP offices or GI clinic
- ❖ SCREEN (DAY -7 -> DAY 0)
 - More thorough screening questions and scheduling by RC (<24 hours)
 - Performed by Telephone
- ❖ ENROLL (DAY 0)
 - Signed Informed Consent procedure, more detailed questions and MCC Procedure performed
 - Occurs at the GWU Medical Faculty Associates Building on [name].
 - NaviCam MCC performed by trained Clinician.
 - Reviewed by a Gastroenterologist.
 - Scheduled for an EGD will ideally be performed within 5 days of the MCC procedure, but will allow MCC procedure to be performed up to 14 days either before or after an EGD (paid by insurance as standard of care).
- ❖ FOLLOW-UP (DAY 1-30)

- Day 7 and Day 30: Telephone Call plus CRISP Chart Review, only if lost to follow-up.

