14. STUDY OVERSIGHT

A Data Safety Monitoring Board (DSMB) consisting of appropriately qualified independent experts has been appointed by the PI to provide review of data on patient safety and study progress. The membership roster is maintained by site PI and study coordinator and is available from them as needed. PI will provide reports including adverse events.

The Data and Safety Monitoring Board provides ongoing evaluation of the study progress including patient accrual and retention, monitoring of adverse events, and the adequacy and efficiency of the analysis plan to discern outcomes that might require study modifications, or result in early cessation of the study due to its benefits or harms. The DSMB does not evaluate the scientific merit or methodology of the study, nor does it directly participate in the execution of a study's protocol, monitor the budget, or approve sub-protocols or other modifications to the study.

The major responsibilities of the Board are:

- To review the data analysis plan and make recommendations for additions or changes to the plan.
- To assess the performance of the site and make appropriate recommendations regarding continuation, probationary status, or termination.
- To consider patient accrual, overall study progress (timeline and follow-up participation), adverse effects and patient safety, and proper monitoring and reporting by the study team as these affect the ethical treatment of participants or the ethical conduct of research.
- Report to the PI on any perceived problems with study conduct, enrollment, sample size, and data collection.

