19.3. Schedule and Content of Reports

The recruitment and follow-up period will begin in November 2019 and continue through October 2021. Data queries will be generated and resolved during this time period through August 2022. Data close-out will be performed immediately following the end of the recruitment period.

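### Section 10.4.3 stops all data collection on termination or suspension, which on its wording also ends the 30-day safety calls for participants who have already swallowed a capsule

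*Protocol*

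**What the plan says.** The whole of section 10.4.3, which covers both premature termination and suspension, is: "Notification of all study subjects. No further data collection".

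Elsewhere the protocol sets up a 30-day safety assessment:

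- Section 7.2 lists as a secondary objective "To measure 30-day safety".
- Section 8.2 lists as a secondary outcome "30-day follow-up for adverse events and safety".
- Section 9.4 (summary of research strategy) gives the source of these data: "Day 7 and Day 30: Telephone Call plus CRISP Chart Review, only if lost to follow-up". Item 7 of the study procedure says that the contacts check for symptom resolution and adverse events.
- Appendix B lists the two calls as study forms (Magnet 7 and Magnet 8), the chart review as Magnet 9 and the adverse event form as Magnet 10.

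Early stopping is foreseen. Section 14 has the DSMB look for outcomes that might "result in early cessation of the study due to its benefits or harms".

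**The concern.** The Day 7 and Day 30 calls are data collection by the protocol's own account: they have numbered forms, and section 8.3.7 lists questions asked on them. A rule that ends all data collection therefore ends the calls, including those to participants who took the capsule days before the stop. No section of the protocol text keeps them running.

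The loss matters most after a stop for harm, because the safety of participants already exposed is then the main open question. Their 30-day outcome would be incomplete and would rest on what they chose to report. Section 6.3.1 says that a retained capsule often causes no symptoms, so volunteered reports are a weak substitute for a scheduled question. The Day 7 and Day 30 forms ask whether the participant noticed the capsule pass (section 8.3.7).

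A suspension is less damaging. Calls falling due while it lasts may be late or missed, depending on its length.

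**Working it through.** The protocol states no figure on this point, so there is none to reproduce. The calculation only shows the scale.

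**Inputs**

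- Planned enrolment: 72 (section 4).
- Follow-up contacts: Day 7 and Day 30 (section 9.4).
- Accrual. The protocol's timelines differ, so all three are used:
  - Section 19.3: "The recruitment and follow-up period will begin in November 2019 and continue through October 2021". From 1 November 2019 to 31 October 2021 is 731 days. Less 30 days for the last participant's follow-up, that leaves 701 days of enrolment.
  - Section 4, "Estimated Time to Complete": 12 months, taken as 365 days of enrolment, or as 335 if the last 30 days are follow-up only.
  - Section 4: "We currently anticipate enrolling 2-3 patients per week over 30 weeks". Exactly 72 over 30 weeks is 72/30 = 2.4 per week.
- Capsule retention: below 1% (section 6.3.1).

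**Formulas**, for a stop during steady accrual, with *r* participants enrolled per day:

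- Participants inside the 30-day window = 30*r*.
- Calls outstanding = 37*r*. Those enrolled less than 7 days ago (7*r*) have two calls to come, and the other 23*r* have one: 14*r* + 23*r* = 37*r*.
- Share of those in the window who are past Day 7 and would lose only the Day 30 call = 23/30 = 77%.
- Share of all enrolled, if the stop comes at half enrolment (72/2 = 36) = 30*r*/36. The protocol names no such stopping point; 36 is an assumption for illustration.

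**Results**

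| Timeline | Per week | In window | Calls outstanding | Share of 36 |
|---|---|---|---|---|
| Section 19.3: 72 in 701 days | 0.72 | 3.1 | 3.8 | 8.6% |
| Section 4: 72 in 365 days | 1.38 | 5.9 | 7.3 | 16.4% |
| Section 4: 72 in 335 days | 1.50 | 6.4 | 7.95 | 17.9% |
| Section 4: 2 per week | 2 | 8.6 | 10.6 | 23.8% |
| Section 4: 72 in 30 weeks | 2.4 | 10.3 | 12.7 | 28.6% |
| Section 4: 3 per week | 3 | 12.9 | 15.9 | 35.7% |

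First row written out: *r* = 72/701 = 0.1027; 30 × 0.1027 = 3.1; 37 × 0.1027 = 3.8; 3.1/36 = 8.6%.

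The share falls as the number enrolled at the stop rises. Against the full 72, the same window counts at 2 to 3 per week are 8.6/72 = 12% to 12.9/72 = 18%.

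**Expected retentions among those in the window**, as upper bounds: 0.01 × 3.1 = 0.03 to 0.01 × 12.9 = 0.13.

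**The case against.** The strongest reply is that nothing here is contradictory. Sections 7.2, 8.2 and 9.4 describe the study running to plan, while section 10.4.3 is a contingency clause in note form that naturally displaces the schedule. Safety duties sit elsewhere and have no stated end at termination. Section 6.3.1 keeps the investigator available to participants around the clock, and sections 12.3 and 12.4 require adverse event reporting. Section 6.3.1 also provides for imaging or a capsule locator when passage is uncertain, and section 9.4 tells participants to return if concerning signs appear. After a suspension is lifted, chart review of those lost to follow-up could recover some events. The numbers are small and depend on a stop of unknown probability, and no formal inference is planned (section 13.2).

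Much of this stands and limits the weight of the point. Volunteered events would still have a reporting route, a suspension does less harm than a termination, and no planned conclusion turns on the lost data.

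It does not answer the point itself. Section 10.4.3 is not silent; it gives a positive instruction, and staff who follow it would stop calling. The reporting duties cover events that come to light and do not keep the scheduled questions going. Chart review is also data collection, so the same clause ends it on termination. An analysis plan cannot recover contacts that were never made.

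**Conclusion.** The concern holds, as a minor one. As written, section 10.4.3 removes the planned 30-day safety ascertainment for participants already exposed when the study stops, including after a stop for harm. Depending on which of the protocol's timelines applies, that is about 3 to 13 participants and 4 to 16 calls. If the stop came at 36 enrolled, it would be about 9% to 36% of them.

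These figures assume even accrual, a stop after at least 30 days of enrolment, and one capsule per participant on the day of enrolment. They are conditional on a stop. They also read section 9.4 as calls to everyone, with chart review only for those lost to follow-up; the sentence in item 7 of the procedure is garbled, but this is its natural sense. Fewer than 0.03 to 0.13 retentions would be expected among those affected. Retention is only one of the major events that section 6.3.1 lists, so this does not measure all the safety information lost.

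**What to change.** Reword section 10.4.3 so that on termination or suspension enrolment and new study procedures stop, while the already planned Day 7 and Day 30 safety calls (Magnet 7 and 8) and adverse event recording (Magnet 10) are completed for every participant who has ingested a capsule and has not withdrawn consent. This brings the clause into line with sections 7.2, 8.2 and 9.4 and leaves intact the rule in section 10.4.2 against contact after withdrawal. It concerns data collection only and changes no clinical rule.

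The cost is a wording change in the protocol, with matching consent text where needed (the consent form was not available for this review). If a stop occurs, there are also about 4 to 16 calls that were planned anyway. No new form, procedure or staff is required.

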11. DATA ENTRY SYSTEM

For this protocol, REDCap database will be used for data entry screens corresponding to the study forms that will be developed and maintained by GWU. Clinical center staff will enter de-identified data into the REDCap database.

12. ASSESSMENT OF SAFETY

12.1. Unanticipated Adverse Events

An unanticipated adverse event is an effect on health or safety caused by, or associated with, a device, if that effect or problem was not previously identified in nature, severity, or degree of incidence in the protocol, or any other unanticipated problem associated with a device that relates to the rights, safety, or welfare of subjects in the clinical study.

12.2. Assessment of Adverse Events

All adverse events will be graded for severity as follows:

Mild: Sign or symptom, usually transient, requiring no special treatment and generally not interfering with usual activities.

Moderate: Sign or symptom, which may be ameliorated by simple therapeutic measures; yet, may interfere with usual activity.

Severe: Sign or symptom that are intense or debilitating and that interfere with usual activities. Recovery is usually aided by therapeutic measures.

The relationship of the adverse event to the study device is defined as follows:

Probably related: Follows a reasonable temporal sequence from study device use delivery/retrieval and cannot be reasonably explained by known characteristics of the subject's clinical data.

Possibly related: Follows a reasonable temporal sequence from study device delivery/retrieval but could have been produced by the subject's clinical state regardless of the study device.

Not related: No relationship to study device activation is perceived.

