6.2. Rationale

In the United States, upper endoscopy is frequently performed for a variety of symptoms including heartburn, bloating, nausea, burping, and epigastric pain/burning. The prevalence of these symptoms may provide as much as 25% of a gastroenterologist's office practice. In general, the diagnostic yield of an EGD is low. Without alarm symptoms, as many as 70% of procedures are negative for significant findings. One major indication is testing for *H. pylori* for which EGD may be unnecessary, because *H. pylori* detection can be accomplished by fecal antigen testing or breath testing as accurately as biopsy and less expensively.

We believe there is an opportunity to improve the risk stratification of patients that undergo endoscopy through the use of MCC. Our primary hypothesis is that MCC allows for visualization of the stomach of symptomatic patients referred from the emergency, urgent care and primary care settings with clinical symptoms appropriate for endoscopy. A prospective study is proposed to evaluate the feasibility, safety and accuracy of this novel diagnostic modality.

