Finally, the study has a low economic risk since the device and the interpretation of the device are not being billed to the subject or his/her insurance company. The follow-up EGD is considered standard of care and will be billed to the patient's insurer. AnX Robotica, the manufacturer of the NaviCam has agreed to cover the cost of medical care and treatment for research injuries sustained by subjects enrolled in the study in accordance with the terms of the Clinical Trial Agreement and there is no economic risk expected as a result of unanticipated complications of the device as these will be covered by AnX Robotica, per the final negotiated terms in the Clinical Trial Agreement (currently under negotiation).

Major adverse events that occur will be reported directly to the principal investigator and overall study coordinator within 24 hours. Minor adverse events include inability to tolerate the MCC capsule, discomfort swallowing capsule, issues regarding video capture, issues regarding video transmission, erroneous video interpretation that has no significant impact on clinical care, protocol deviations, reactions to medication (promotility agent), delays in endoscopy interpretation, delays in EGD and others. All minor adverse events will be shared with the entire research team at regularly scheduled monthly calls or sooner at the PI's discretion.

Any major adverse events that occur will be reported directly to the principal investigator who will be available to study subjects 24 hours a day. Severe adverse events will be reported to the entire research team, the sponsor, the DSMB and to IRB within 24 hours. Updates will be provided after a full investigation is completed. SAE's will also be reported to the FDA. Potential major adverse events include delayed definitive care, and capsule retention in the small bowel, and any serious outcome that may be related to study protocol. A DSMB will be formed that includes experts in primary care, emergency medicine, and gastroenterology and research methodology. DSMB of approximately 3-5 multi-disciplinary persons will meet every 6 months during which a report will be produced by PI and as needed for SAE's.

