9.3. Patient Safety

The study will be conducted in compliance with the Declaration of Helsinki, ICH-GCP guidelines, ISO 14155, and US regulations. Study design will be approved by the local IRB at each participating institution prior to commencement.

9.4. Study procedure:

1. Screen potential adult patients with an appropriate indication for upper endoscopy such as epigastric pain/burning, nausea and or vomiting, bloating, heartburn, iron deficiency anemia, unintended weight loss, abnormal imaging suggesting organic disease from a larger pool of patients seen in an ED, Urgent Care, Primary Care and GI Clinic patients. In some settings, a research assistant will be on site to perform the screen. In other settings, the clinical staff will perform the screen or potential patients will be contacted by phone by RC. (Form used: *Magnet 1*)
2. Patients screened who are eligible will be approached about potential interest. (See *full list of inclusion/ exclusion criteria*). In some circumstances, patients will be given contact information for the research coordinator (RC), who will contact them as soon as possible to schedule MCC. In other circumstances, the research assistant will contact RC and attempt to schedule MCC before patient leaves the clinical setting.
3. RC will contact patients to complete screening, confirm eligibility, obtain verbal consent, and schedule both MCC and EGD (if EGD is not already scheduled). Formal written consent will be obtained by patient at the MCC location ([name]).
4. Participants arrive at the MCC location for final screen, sign written consent and undergo MCC. All consented patients will be given a study ID and recorded in enrollment log. (Form used: *Magnet 3*) The patient's demographics and images will be stored in a HIPAA compliant fashion.
 - BRIEF DESCRIPTION OF MCC PROCEDURE. The patient will be NPO midnight. They will come to the facility and will ingest the capsule per manufacturer's protocol. (Manufacturer's protocol says that the person will take 10ml of simethicone in 100ml of water 40min before capsule is ingested. The capsule will then be controlled externally by magnetic field by the examining health care provider in such a way that the major regions of the stomach are photo-documented with still images and video. This may involve changing the position of the patient and the

possible ingestion of additional water. The sequence of the examination

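### Adverse events are graded only against the capsule device, although the planned EGD normally falls inside the 30-day safety window, so ambiguous events cannot be attributed to EGD or sedation

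*Protocol*

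**What the plan says.** The Rationale (Section 6.2) gives the study's purpose: "A prospective study is proposed to evaluate the feasibility, safety and accuracy of this novel diagnostic modality". Section 7.2 makes 30-day safety a secondary objective, and Section 8.2 lists the outcome as "30-day follow-up for adverse events and safety".

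The clock is set in Section 9.4, under the Summary of Research Strategy. Day 0 is the enrolment day: "Signed Informed Consent procedure, more detailed questions and MCC Procedure performed". Follow-up is Day 1 to Day 30, with telephone contacts on Days 7 and 30. No contact is timed from the EGD. The EGD should ideally come within 5 days of MCC, but the plan "will allow MCC procedure to be performed up to 14 days either before or after an EGD". Section 13.2 has all 72 participants receive MCC and then be referred for EGD.

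Section 12.2 introduces its grades with "The relationship of the adverse event to the study device is defined as follows" and offers three: probably, possibly and not related. An event is possibly related if its timing fits but it "could have been produced by the subject's clinical state regardless of the study device". The *probably related* grade is withheld only if the subject's known clinical data explain the event. EGD and sedation appear in none of the definitions.

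On preparation, Section 9.4 describes "10ml of simethicone in 100ml of water 40min before capsule is ingested", whereas Section 6.3.1 lists among minor adverse events "reactions to medication (promotility agent").

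**The concern.** The safety result is meant to inform on MCC, but most participants should have a second procedure within days of it. Section 6.1 says that capsule endoscopy carries significantly less risk than EGD, and Sections 6.1, 6.3.3 and 8.3.1 link EGD with anesthesia or sedation. A symptom that appears after both tests may come from either. The only scale provided asks about the device and names the patient's own condition as the sole alternative. An assessor who follows it literally has no place to record that EGD or sedation is the likelier cause.

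Two things are at stake. One is the grading of ambiguous events, which also matters because Section 12.4 ties one reporting route to device-related serious events (Section 6.3.1 reports serious events more widely). The other is the plain 30-day event count, whose content depends on which test came first. If attribution and timing relative to EGD are not recorded when the event occurs, no later analysis can restore them.

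**Working it through.** The protocol gives no safety rate, alpha or power to reproduce; Section 13.2 says that 72 is a practical choice. The check is therefore calendar arithmetic on the protocol's own windows, followed by an illustration.

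**Step 1. Post-EGD time inside the window.** Inputs from Section 9.4: MCC on Day 0, follow-up to Day 30, EGD on day *d* from −14 to +14. The post-EGD days covered run from max(0, −*d*) to 30 − *d*.

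| EGD on day | Post-EGD days covered | Days after MCC but before EGD |
|---|---|---|
| +1 | 0 to 29 | 1 |
| +5 | 0 to 25 | 5 |
| +14 | 0 to 16 | 14 |
| −1 | 1 to 31 | none |
| −5 | 5 to 35 | none |
| −7 | 7 to 37 | none |
| −14 | 14 to 44 | none |

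MCC first: any EGD on Days 1 to 14 puts the EGD and its first 16 to 29 days inside the window. If the EGD is done by Day 7, which includes the 5-day target, the Day 7 call comes on or after the EGD day, so no call covers MCC alone.

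EGD first: the first 1 to 14 post-EGD days come before Day 0, and also before written consent. With EGD on Day −7 or earlier, none of the first 7 post-EGD days is observed.

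**Step 2. What the scale can express.** Take throat soreness on Day 6 after an EGD on Day 5.

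- *Not related* is available if the assessor sees no link to the device.
- If the assessor is unsure, the timing can still count as reasonable for the device, and the scale then asks only whether the subject's clinical state could explain the event.
- EGD is not offered as an explanation, so the true reason for doubt is not recorded.

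The scale therefore handles clear EGD events and fails on ambiguous ones.

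**Step 3. Possible size.** The documents give no EGD or sedation event risk, so *q* is assumed over a range. For *n* MCC-first participants, expected EGD events in the window = *n* × *q*, and P(at least one) = 1 − (1 − *q*)^*n*.

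| Assumed *q* | Expected, all 72 MCC-first | P(at least one) | Expected, 36 MCC-first |
|---|---|---|---|
| 0.5% | 72 × 0.005 = 0.36 | 30% | 0.18 |
| 1% | 72 × 0.01 = 0.72 | 52% | 0.36 |
| 2% | 72 × 0.02 = 1.44 | 77% | 0.72 |
| 5% | 72 × 0.05 = 3.6 | 98% | 1.8 |

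In the last column, the other 36 are EGD-first. If their EGD events occur promptly, the same expected number falls before Day 0. These figures count EGD events in the window, not misattributed ones; only the ambiguous part is at risk of misattribution.

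**Step 4. Effect of one misattributed event.** With exact (Clopper-Pearson) limits, 0/72 has a 95% interval of 0 to 1 − 0.025^(1/72) = 5.0%. One event gives 1/72 = 1.4%, with limits 0.04% to 7.5%.

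**The case against.** The strongest reply is that a device study may properly grade against the device. EGD is standard of care, and *not related* removes clear EGD events from the device-related count. This stands, and it confines the problem to ambiguous events and to the undivided count. One could also stretch clinical data or clinical state to cover a recent EGD, but Section 12.2 does not say so, and assessors may differ.

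Section 6.3.1 looks beyond the device when it speaks of serious outcomes related to the study protocol. That covers major events only. The adverse event form (Magnet 10) is listed but not shown and may already hold the needed fields, so the fix is conditional on that.

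An analysis plan could split the tables. It could not supply an attribution that was never collected.

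A reader might infer four stronger things that the documents do not support:

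- **EGD-first participants contribute no EGD events.** They lose the early post-EGD days; later days are covered, for example days 1 to 31 when EGD is on Day −1.
- **A Day 7 call before a Day 8 to 14 EGD is a defect.** For MCC safety it is helpful, since that call reflects MCC alone.
- **Preparation events contaminate MCC safety.** The simethicone drink is part of the MCC procedure, so its reactions belong there.
- **A planned safety comparison of MCC with EGD is spoiled.** None is planned: Section 7.2 compares the two on cost, satisfaction, lesion detection and time, but says only that 30-day safety will be measured.

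**Conclusion.** The point holds in limited form. The causality scale is device-only, the clock runs from MCC, and the intended order and 5-day target put the EGD inside the window for most participants. Ambiguous events after both tests cannot be attributed to EGD or sedation, and the unsplit 30-day count means different things by test order.

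The impact is modest. Safety is a secondary, descriptive outcome in a pilot with no formal inference, and one event shifts the estimate by 1.4 percentage points. That most EGDs follow MCC rests on the stated intention, since the protocol gives no expected split by order. The event risks in the illustration are assumptions, and how many events would be ambiguous is unknown.

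Separately, the promotility agent in Section 6.3.1 and the simethicone preparation in Section 9.4 do not match, and the two sections must be reconciled. This is a text inconsistency and adds nothing to the attribution point.

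**What to change.** 1. In Section 12.2, and on Magnet 10 if not already there, grade each event for relationship to the capsule/MCC procedure (including its preparation) and, alongside it, to EGD/sedation. Name EGD as a possible alternative cause under *possibly related*.
2. Record the onset date of each event against both the MCC date and the EGD date.
3. Report 30-day safety in two parts, by test order: events from MCC until EGD, and all events to Day 30. For EGD-first participants only the second part applies. For MCC-first participants who never have the EGD, the first part runs to Day 30.
4. Reconcile Sections 6.3.1 and 9.4 on the medication given with MCC.

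The cost is about two extra form fields and one table split, with no added visits, calls or procedures. The drawback is that the MCC-only interval is short and varies between participants: 1 to 14 days when EGD follows MCC within the allowed window. It should be shown with the table.
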